7.8 Follow-Up

7.8.1 Discharge or Within 12-24 Hours Post-Procedure

The following assessments and procedures will be performed within **12-24 hours** post procedure or prior to hospital discharge, whichever occurs first:

- Follow up visit assessments including:
 - Physical examination
 - Vital signs
 - Height and weight
 - Target review of symptoms
 - Adverse event assessment

7.8.2 30-Day Follow-Up

The following evaluations will be performed at **30 days** (+/-7 days) post procedure:

- Follow-up visit assessments including:
 - Physical examination
 - Vital signs
 - Height and weight
 - Target review of symptoms
 - ABI (at rest or after exercise; keep consistent with screening)
 - Rutherford Category
 - Review of medications

	No.: CP 64007	REV. D
	TITLE: Disrupt PAD+ Study	
	CLASS: CLINICAL PROTOCOL	PAGE 23 OF 57

- Adverse event assessment

Note: If the 30-Day Visit cannot be performed on-site, a remote follow-up visit is acceptable. If visit is conducted remotely, ABI is not required (will not incur a protocol deviation).

7.8.3 6-Month Follow-Up

The following evaluations will be performed at **6 months** (+/-30 days) post procedure:

- Follow-up visit assessments including:
 - Physical Examination
 - Vital signs
 - Height and weight
 - Target review of symptoms
 - ABI (at rest or after exercise; keep consistent with screening)
 - Rutherford Category
 - Review of medications
 - Adverse event assessment

Note: If the 6-Month Visit cannot be performed on-site, a remote follow-up visit is acceptable. If visit is conducted remotely, ABI is not required (will not incur a protocol deviation).

7.8.4 12-Month Follow-Up

The following evaluations will be scheduled for **12 months** (+/-30 days) post procedure:

- Follow-up visit assessments including:
 - Physical Examination
 - Vital signs
 - Height and weight
 - Target review of symptoms
 - ABI (at rest or after exercise; keep consistent with screening)
 - Rutherford Category
 - Review of medications
 - Duplex Ultrasound
 - Adverse event assessment

7.8.5 Prior to Target Limb Revascularization

The following evaluations will be completed prior to any target limb revascularization to assess symptoms and functional status prior to revascularization:

- Physical Examination
 - Vital signs
 - Height and weight
 - Target review of symptoms
- ABI (at rest or after exercise; keep consistent with screening)

	No.: CP 64007	REV. D
	TITLE: Disrupt PAD+ Study	
	CLASS: CLINICAL PROTOCOL	PAGE 24 OF 57

- Rutherford Category
- Review of medications
- Angiographic lesion assessment (Angiographic images for revascularization procedures associated with the target limb must be submitted to the core lab.)

7.9 Subject Withdrawal

A study subject has the right to discontinue participation at any time without penalty or loss of benefits to which the subject is otherwise entitled. A subject that has withdrawn from the study will be treated according to standard of medical care and will not be replaced.

7.9.1 When and How to Withdraw Subjects

Subjects may be withdrawn with the medical discretion of the physician, or they may voluntarily withdraw their consent at any time without impact to their medical treatment. When a subject is withdrawn, all data obtained prior to the time of withdrawal may be submitted to the Study Sponsor and be included in the study database, unless otherwise requested by the subject in writing.

In the event a subject is lost to follow-up or cannot be contacted for post-treatment assessments, at least three attempts (two phone calls and a certified letter) will be made to locate the study subject, and these efforts will be documented. If the subject cannot be located, the subject's lost to follow-up status will be documented in the EDC and they will be exited from the study.

Should the subject expire, an adverse event and study exit/withdrawal form should be completed. Physician assessment is required to determine if the cause of death was possibly or definitely related to the M⁵⁺ IVL System. If available, copies of the death certificate and/or an autopsy report should be included in the research records. The Investigator may need to provide written notification to the IRB/EC upon the death of the study subject, dependent on the IRB/EC policies.

	No.: CP 64007	REV. D
	TITLE: Disrupt PAD+ Study	
	CLASS: CLINICAL PROTOCOL	PAGE 25 OF 57

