7.4 Schedule of Events and Evaluations

Table 1 lists the schedule of events and evaluations required for the study.

Table 1. Study Schedule of Events

	Screening/ Baseline ²	Enrollment and Procedure	Discharge ³	30 Days ⁴ (+/- 7 days)	6 Months ⁴ (+/- 30 days)	12 Months (+/- 30 days)	Pre-Target Limb Revasc
Informed Consent	X ¹						
Medical History	X						
Physical Examination	X		X	X	X	X	X
Baseline labs	X						
Pregnancy test	X						
Ankle Brachial Index (ABI)	X			X ⁵	X ⁵	X	X
Rutherford Category (RC)	X			X	X	X	X
Angiographic Lesion Assessment		X					X
IVL Procedure		X					
Duplex Ultrasound						X	
Medication regimen per protocol			X	X	X	X	X
Adverse Event Assessment		X	X	X	X	X	X
OCT or IVUS (optional)		X					

¹ Consent to be obtained within 30 days prior to procedure.

² Evaluations may be done up to 30 days before the procedure with the exception of ABI, which may be completed within 60 days of the procedure.

³ Examinations are to be completed within 12-24 hours post-procedure or prior to discharge, whichever comes first.

⁴ 30-Day and 6-month visit can be conducted as an on-site or remote visit.

⁵ ABI should be assessed if visit is conducted on-site.

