9.4 Handling of Dropouts or Missing Data

No imputation of or adjustments for missing data will be performed for the primary analyses. All available data will be presented. For time to event analyses, subjects will be censored at their last known follow-up.

	No.: CP 64007	REV. D
	TITLE: Disrupt PAD+ Study	
	CLASS: CLINICAL PROTOCOL	PAGE 28 OF 57

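### A subject who cannot be located may be exited well before 12 months, and the 12-month visit has no remote fallback, so obtainable late follow-up data may never be sought

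*Combined protocol and SAP*

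**What the plan says.** Section 7.9.1 sets the rule for subjects who drop out of contact. The trigger is "In the event a subject is lost to follow-up or cannot be contacted for post-treatment assessments". The effort required is that "at least three attempts (two phone calls and a certified letter) will be made to locate the study subject". If the subject still cannot be found, "the subject's lost to follow-up status will be documented in the EDC and they will be exited from the study". For withdrawn subjects the same section says that, unless the subject objects in writing, "all data obtained prior to the time of withdrawal may be submitted to the Study Sponsor and be included in the study database".

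On remote visits, footnote 4 to Table 1 (section 7.4) says "30-Day and 6-month visit can be conducted as an on-site or remote visit". The notes in 7.8.2 and 7.8.3 repeat the option for those two visits. Section 7.8.4, for 12 months, has no such note, and footnote 4 is not attached to the 12-month column.

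The endpoints concerned are secondary (5.2): MAE at 6 and 12 months, and clinically driven TLR and change in Rutherford category at 30 days, 6 and 12 months. Sections 10.4.1 and 10.4.2 call for adverse and serious adverse events to be collected from enrollment to 12 months.

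On missing data, section 9.4 says "No imputation of or adjustments for missing data will be performed for the primary analyses". It adds that all available data are presented and that time-to-event analyses censor at last known follow-up.

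**The concern.** The exit rule is tied to failure to locate the subject, not to a point in follow-up. A site that cannot find a subject around the 30-day or 6-month visit complies with 7.9.1 by exiting the subject then, although the subject has not withdrawn consent and might be reachable later. That sits awkwardly with adverse event collection to 12 months and with the 6- and 12-month endpoints.

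The 12-month gap concerns a different group: subjects who can be reached but cannot attend. Duplex ultrasound, ABI and the physical examination need attendance. Event history, TLR and Rutherford category do not; the plan already accepts remote contact for them at the two earlier visits.

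What is at stake is avoidable missing data in the late secondary endpoints. Subjects who are in hospital or have been re-treated elsewhere are plausible non-responders. If loss is related to outcome, neither presenting available data nor censoring removes the resulting bias.

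**Working it through.** **1. The plan's own figure.** Section 9.2 gives a 95% interval of [48.3, 79.4] for 65% success in 40 lesions. With 0.65 × 40 = 26 successes, the exact (Clopper-Pearson) interval for 26/40 is 48.3% to 79.4%, so the figure reproduces. (Wald gives 50.2 to 79.8 and Wilson 49.5 to 77.9.) This confirms the exact method stated in 9.1. The interval concerns success at the index procedure, so late exits do not touch it.

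**2. The passages side by side.**

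| Question | What the plan provides |
|---|---|
| When may a subject be exited as lost? | Whenever not located after at least three attempts; no timing condition (7.9.1) |
| Is contact required at later windows? | Not stated |
| Can the subject re-enter? | Not stated |
| Are other sources checked before exit? | Not stated |
| Remote visit at 30 days and 6 months? | Yes (Table 1 footnote 4; 7.8.2, 7.8.3) |
| Remote visit at 12 months? | Not stated (7.8.4) |
| Are data already held kept? | They may be, for withdrawn subjects (7.9.1); all available data are presented (9.4) |

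**3. Possible size.** The documents give no dropout rate and no 12-month event rate, so exits and events are assumed. The inputs are 40 subjects (the maximum in 9.2), x = 2 observed events, and m exits with unknown outcome, from 0 to 8 (0% to 20%).

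- Observed rate: x / (40 − m), with exact 95% interval.
- Lowest possible full-cohort rate (no exited subject has an event): x / 40.
- Highest possible (every exited subject has one): (x + m) / 40.
- Width of that range: m / 40, which is 2.5 percentage points per exit.

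| Exits m | Observed rate | Exact 95% interval | Full-cohort range |
|---|---|---|---|
| 0 | 2/40 = 5.0% | 0.6 to 16.9 | 5.0% |
| 2 | 2/38 = 5.3% | 0.6 to 17.7 | 5.0% to 10.0% |
| 4 | 2/36 = 5.6% | 0.7 to 18.7 | 5.0% to 15.0% |
| 8 | 2/32 = 6.3% | 0.8 to 20.8 | 5.0% to 25.0% |

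The loss of precision is modest: with 8 exits the upper limit moves from 16.9% to 20.8%. The larger effect is the unknown outcome of the exited subjects, which leaves a 10-point range at 4 exits and a 20-point range at 8.

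**The case against.** The strongest case on the other side is that the plan is less severe than a quick reading suggests, and much of this stands.

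- A reader might infer that one missed visit means permanent exit after two calls and a letter. The trigger refers to assessments in the plural and sets no number of missed visits, three attempts is a minimum, exit follows only if the subject cannot be located, and nothing says exit is irreversible. The text permits early exit; it does not order it after a single miss.
- A reader might infer that data are discarded by rule. They are not: earlier data may be kept, all available data are presented, and time-to-event analyses censor at last contact. The sentence ruling out imputation covers only the primary analyses.
- A reachable subject who cannot travel at 12 months is not exited. Adverse event collection continues, serious events are reportable whenever the site learns of them, and target-limb revascularization has its own unscheduled assessment (7.8.5).
- Late MAE is less exposed than it looks. Death is not an MAE component, section 15.1 limits unplanned amputation to the first 30 days, and perforation is mainly procedural.
- On-site attendance at 12 months has a purpose: duplex ultrasound is scheduled only then, and ABI is required then.
- Asking outside physicians about a lost subject raises consent questions; section 11.4 makes even informing the personal physician depend on the subject's approval or national rules.

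None of this supplies the missing provisions. No section requires later contact, allows re-entry, names another source for unlocated subjects, or provides a remote fallback at 12 months. Censoring and presenting available data describe how to analyze what was collected; they do not prompt anyone to collect more.

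**Conclusion.** The point holds in limited form. A site following the plan may stop seeking data on a consenting subject before 12 months, and the plan provides no remote route to obtainable 12-month information. TLR, adverse event and Rutherford data at 6 and 12 months are the most exposed, and MAE less so.

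The size rests on assumed counts: each exit leaves 2.5 percentage points of uncertainty in a 40-subject proportion, and 4 exits with 2 observed events leave a range of 5.0% to 15.0%. With fewer than 40 subjects, each exit weighs more.

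A reader might go further and infer that TLR would be under-reported by about half, for example 2/36 = 5.6% [0.7, 18.7] against a true 4/40 = 10.0% [2.8, 23.7]. The documents do not support that. It assumes that 2 of 4 missed subjects (50%) had a TLR against 5.6% of those followed, a nine-fold difference with no source in the plan. The direction of bias is plausible; its size is unknown.

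The consequence is modest. The study is descriptive, the affected endpoints are secondary, technical success is settled at the index procedure, and the 30-day visit that supports primary MAE already has a remote option. The change is worth making because it is cheap and because data not sought in the window may not be recoverable.

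**What to change.** 1. **Section 7.9.1.** When a subject cannot be contacted for a visit, record that visit as missed, keep the subject in the study, and attempt contact again at each later window. Declare loss to follow-up only when the 12-month window closes, after checking the site's own records where consent permits.
2. **Section 7.8.4 and Table 1 footnote 4.** When on-site attendance at 12 months is impossible, allow remote collection of AE/MAE, TLR and Rutherford category, with DUS and ABI recorded as missing.

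The cost is amendment wording, which goes through the IRB/EC submission in sections 11.6 and 14.1, and a few extra calls and record checks by existing staff. Treatment, sample size and analysis methods do not change. The downside is a small risk that sites default to remote 12-month visits and lose ultrasound data; restricting the option to subjects unable to attend limits it.

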8.0 BENEFITS AND RISKS

8.1 Benefits

There are no guaranteed benefits from participation in the study. The study will provide safety and performance data associated with M⁵⁺Peripheral IVL System treatment of calcified iliac and femoropopliteal arteries. These clinical results may inform physicians in determining the optimal treatment strategy for this patient population.

8.2 Risks

For detailed information on the risks of the devices used in the study procedure, including a complete list of warnings, precautions and potential adverse events, please refer to the Instructions for Use (IFU) for the M⁵⁺Peripheral IVL System. It is important to ensure that the IFU referred to represents the generation of the device used in the study procedure.

8.3 Mitigation of Risks

Only those patients meeting each inclusion and no exclusion criteria will be enrolled into this study. Investigators will be qualified by education, training and experience to assume responsibility for the proper conduct of the clinical investigation. Risks of observed or theoretical adverse events will be mitigated through the Instructions for Use, physician training, patient selection in the study protocol and close monitoring of protocol adherence.

All efforts will be made to minimize risks specifically by:

- Site selection
- Ensuring compliance to the protocol and IFU
- Study monitoring
- Safety processes – protocol adverse event reporting requirements, CEC and data safety monitoring committee oversight, and safety reporting to regulatory authorities including Vigilance reporting

	No.: CP 64007	REV. D
	TITLE: Disrupt PAD+ Study	
	CLASS: CLINICAL PROTOCOL	PAGE 26 OF 57

9.0 DATA ANALYSIS PLAN

9.1 General Statistical Methods

Descriptive statistics will be provided in this study. Analyses will be conducted at pre-specified time points including 30 days, 6 and 12 months.

Categorical data will be summarized using frequency tables, presenting the subject counts and percentages. McNemar's chi-square may be used to assess within-subject changes in a bivariate response variable.

Continuous variables will be summarized by the mean, standard deviation, median, minimum and maximum. Within-subject changes will be analyzed parametrically using the Paired t-test if the differences are normally distributed, or non-parametrically using the Sign-Rank Test if the differences are not normally distributed.

Exact confidence intervals will be generated for estimates of proportions. Asymptotic confidence intervals will be generated for estimates of means. The p-values of all tests will be reported without any correction for the multiplicity of tests performed.

Statistical analyses will be performed using SAS System® Version 9.4. Analyses will be performed on all subjects enrolled in the study cohort.

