Primary Performance Endpoint:	
 • Technical success defined as final residual stenosis $\leq 30\%$ without flow-limiting dissection (\geq Grade D) of the lesion by angiographic core lab
Secondary Endpoints:	
 • IVL Technical success defined as residual stenosis $\leq 30\%$ without flow-limiting dissection (\geq Grade D) of the lesion post-IVL by angiographic core lab • Procedural success defined as final residual stenosis $\leq 30\%$ without any flow-limiting dissection (\geq Grade D) in all target lesions by angiographic core lab • Major Adverse Events (MAE) at 6 and 12 months • Primary patency at 12 months defined as freedom from clinically-driven target lesion revascularization (TLR) and freedom from restenosis determined by duplex ultrasound or angiogram $\geq 50\%$ stenosis • Clinically-driven target lesion revascularization (TLR) at 30 days, 6 and 12 months • Ankle-brachial index (ABI) at 12 months, reported as change from baseline • Rutherford Category at 30 days, 6 and 12 months, reported as change from baseline
Study Inclusion Criteria:	
General Inclusion Criteria
 
 1. Subject is able and willing to comply with all assessments in the study. 2. Subject or subject's legal representative have been informed of the nature of the study, agrees to participate and has signed the approved consent form. 3. Age of subject is > 18. 4. Rutherford Clinical Category 2, 3, 4 or 5 of the target limb(s). 5. Estimated life expectancy > 1 year.

	No.: CP 64007	REV. D
	TITLE: Disrupt PAD+ Study	
	CLASS: CLINICAL PROTOCOL	PAGE 8 OF 57

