	
9. Subject has acute or chronic renal disease defined as serum creatinine of >2.5 mg/dL or >220 umol/L, unless on dialysis.
 
10. Subject is pregnant or nursing.
 
11. Subject is participating in another research study involving an investigational agent (pharmaceutical, biologic, or medical device) that has not reached the primary endpoint.
 
12. Subject has other medical, social or psychological problems that, in the opinion of the investigator, preclude them from receiving this treatment, and the procedures and evaluations pre- and post-treatment.
 
13. The planned use of specialty balloons, re-entry or atherectomy devices in the target lesion(s).
 
Angiographic Exclusion Criteria
 
14. In-stent restenosis within 10mm of the target zone.
 
15. Target lesions distal to the popliteal artery.
 
16. Evidence of aneurysm or thrombus in target vessel.
 
17. No calcium or mild calcium in the target lesion.
 
18. Target lesion within native or synthetic vessel grafts.
 
19. Subject has more than three target lesions requiring treatment.
 
20. Subject has significant non-target lesion (>50% stenosis or occlusion) within the target limb (e.g. iliac, common femoral or below-the-knee) not successfully treated prior to treatment of the target lesions.
 
21. Failure to successfully cross the guidewire across the target lesion; successful crossing defined as tip of the guidewire distal to the target lesion in the absence of flow limiting dissections or perforations.

Study Statistical Methods:	Descriptive statistics will be reported.
Study Sponsor/Study Management Contact:	
Shockwave Medical, Inc. [name] [name] USA
 
Contact: [name] Title: Senior Director, Clinical Affairs Telephone: (direct): [contact] Email: [contact]

	No.: CP 64007	REV. D
	TITLE: Disrupt PAD+ Study	
	CLASS: CLINICAL PROTOCOL	PAGE 10 OF 57

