5.1 Primary Endpoint(s)

Primary Safety Endpoint

Major Adverse Events (MAE) at 30 days defined as:

- Need for emergency surgical revascularization of target limb
- Unplanned target limb major amputation (above the ankle)
- Symptomatic thrombus or distal emboli that require surgical, mechanical or pharmacologic means to improve flow and extend hospitalization
- Perforations that require an intervention, including bail-out stenting

Primary Performance Endpoint(s)

Technical success is defined as final residual stenosis $\leq 30\%$ without flow-limiting dissection (\geq Grade D) of the lesion by angiographic core lab.

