5.2 Secondary Endpoint(s)

Performance

- IVL Technical success is defined as residual stenosis $\leq 30\%$ without flow-limiting dissection (\geq Grade D) of the lesion post-IVL by angiographic core lab.
- Procedural success is defined as final residual stenosis $\leq 30\%$ without any flow-limiting dissection (\geq Grade D) in all target lesions by angiographic core lab.

Safety

- MAE at 6 and 12 months

Patency

- Primary patency at 12 months defined as freedom from clinically-driven target lesion revascularization (TLR) and freedom from restenosis determined by duplex ultrasound or angiogram $\geq 50\%$ stenosis. Acute PTA failure requiring a stent of the target lesion at any time during the index procedure will be counted as a loss of primary patency.
- Clinically driven target lesion revascularization (TLR) at 30 days, 6 and 12 months

Clinical

- Ankle-brachial index (ABI) at 12 months, reported as change from baseline
- Rutherford Category at 30 days, 6 and 12 months, reported as change from baseline

	No.: CP 64007	REV. D
	TITLE: Disrupt PAD+ Study	
	CLASS: CLINICAL PROTOCOL	PAGE 14 OF 57

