6.2 Number of Subjects

A minimum of 40 lesions in up to 40 subjects with moderate and severely calcified iliac and femoropopliteal artery disease presenting with Rutherford Category 2 to 5 will be enrolled. Each site will be allowed to enroll a maximum of 12 subjects. Multiple lesion treatment with IVL will be allowed and a minimum of twenty (20) lesions across all enrolled subjects must be treated with the 8.0 mm catheter size.

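### Lesion-level success rates get a plain exact interval that ignores up to three lesions coming from the same subject

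*Combined protocol and SAP*

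**What the plan says.** All references are to the combined protocol and SAP.

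- **Unit of the endpoints.** The study summary (2.0) gives the primary performance endpoint as "Technical success defined as final residual stenosis" of at most 30% without flow-limiting dissection. Section 5.1 scores it "of the lesion by angiographic core lab". In 5.2, IVL technical success is scored "of the lesion post-IVL by angiographic core lab". Procedural success is different: it is judged "in all target lesions by angiographic core lab", which makes it a subject-level endpoint.
- **Lesions per subject.** Section 6.2 states that "Multiple lesion treatment with IVL will be allowed". Section 9.2 caps target lesions at three per subject and plans at least 40 lesions in no more than 40 subjects.
- **Analysis.** The summary says "Descriptive statistics will be reported". Section 9.1 adds "Categorical data will be summarized using frequency tables, presenting the subject counts and percentages" and "Exact confidence intervals will be generated for estimates of proportions". Section 9.2 promises a two-sided 95% interval for every endpoint. Sections 9.1 to 9.4 contain no cluster adjustment, no one-lesion-per-subject rule and no sensitivity analysis for within-subject correlation.
- **Planning figure.** Section 9.2 takes 65% for Procedural success, calls it the primary performance estimate, and gives [48.3, 79.4] for 40 lesions.

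**The concern.** An exact binomial interval is valid for independent trials. Two or three lesions in one subject share the same disease, operator and session, so their outcomes may correlate. If they do, 40 lesions carry less information than 40 independent observations and the interval is too narrow.

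The interval is the only planned statement of uncertainty for the primary performance endpoint. Section 9.2 also reads its lower bound against a 50.4% comparator rate.

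A related inconsistency concerns the denominator. Procedural success covers all target lesions in 5.2, the definition in 15.1 omits that condition, and 9.2 applies the term to 40 lesions as though it were the primary endpoint. Section 9.1 speaks only of subject counts, which does not fit a lesion-level endpoint. As written, the denominator of the primary result is not fixed in advance.

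**Working it through.** **1. Reproduce the plan's figure.** The inputs are 65% and 40 lesions (9.2), so x = 26 and n = 40. Clopper-Pearson limits are the 0.025 quantile of Beta(26, 15) and the 0.975 quantile of Beta(27, 14): 48.3% and 79.4%. This matches. Wald (50.2 to 79.8) and Wilson (49.5 to 77.9) do not. The plan therefore treats the 40 lesions as 40 independent trials.

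**2. Assumptions.** The documents give neither the distribution of lesions per subject nor the ICC. Four layouts of 40 lesions are used, with ICC from 0 to 0.5:

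- 35 subjects, five with two lesions
- 30 subjects, ten with two
- 20 subjects, all with two
- 14 subjects, 12 with three and two with two. This is the extreme the three-lesion cap allows, not a projection.

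A fifth layout has 40 subjects supplying 50 lesions (ten with two).

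**3. Exact coverage of the planned interval at 65% success.** Each subject's number of successes is beta-binomial. The distributions are convolved over subjects, and the probabilities of all totals whose Clopper-Pearson interval contains 65% are summed. With ICC 0 and 40 lesions, coverage is 97.0%.

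| Layout | ICC 0.1 | ICC 0.3 | ICC 0.5 | Below 95% above ICC |
|---|---|---|---|---|
| 35 subjects | 96.8% | 96.4% | 96.0% | 0.92 |
| 30 subjects | 96.6% | 95.7% | 94.8% | 0.46 |
| 20 subjects | 96.2% | 94.3% | 92.3% | 0.23 |
| 14 subjects | 95.4% | 91.6% | 87.8% | 0.12 |
| 40 subjects, 50 lesions | 95.9% | 95.2% | 94.3% | 0.34 |

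At 90% success and ICC 0.5, coverage in the four 40-lesion layouts is 95.9, 94.7, 91.7 and 86.5%. For 40 subjects with 50 lesions it is 95.4%, and it falls below 95% only above ICC 0.63.

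**4. Effect on the planning interval.** Design effect = 1 + ICC × (Σm²/Σm − 1), where m is the number of lesions in a subject. Effective n = 40 / design effect. The interval is Clopper-Pearson at 65% of the effective n. At ICC 0.5:

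| Subjects | Σm²/Σm | Design effect | Effective n | 95% interval |
|---|---|---|---|---|
| 40 (one lesion each) | 1.00 | 1.000 | 40.0 | [48.3, 79.4] |
| 35 | 50/40 = 1.25 | 1.125 | 35.6 | [47.2, 80.2] |
| 30 | 60/40 = 1.50 | 1.25 | 32.0 | [46.2, 80.9] |
| 20 | 80/40 = 2.00 | 1.50 | 26.7 | [44.2, 82.3] |
| 14 | 116/40 = 2.90 | 1.95 | 20.5 | [41.1, 84.4] |

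**5. Performance of a cluster-adjusted alternative.** The interval set out under the fix was simulated with 40,000 replicates per setting, estimating the design effect in each replicate. At 65% success it covers 96.5% to 98.3% in every multi-lesion layout for ICC 0 to 0.5. At 90% success it covers 98.5% to 99.2% in the 40-lesion layouts and 97.6% to 98.5% for 40 subjects with 50 lesions.

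**The case against.** The strongest case is that the harm is conditional and may be small. Clopper-Pearson has slack: 97.0% under independence. With 35 subjects the slack absorbs correlation up to ICC 0.92. If every subject has one lesion, which the enrollment target allows, nothing changes. Coverage near 92% or lower needs every subject to have at least two lesions and an ICC near 0.5, or something close to the 14-subject extreme with an ICC of about 0.3 or more. All of this stands and limits the size of the point.

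Nor does any decision rest on the interval. The study is descriptive, with no test, performance goal or success rule. Section 9.2 first justifies n = 40 by a rule of thumb of 12 to 50, and the 50.4% comparison has no stated margin. That also stands, and it keeps the point below a critical one.

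The replacement is conservative where clustering is light. With 35 subjects at 90% success, the planned interval covers 97.0% to 95.9% over ICC 0 to 0.5, and the replacement about 98.6% to 98.8%. This is a real cost. The design-effect floor and the rule for 0% or 100% are choices, and another prespecified cluster-adjusted interval would serve.

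Finally, the Procedural success inconsistency is a separate matter of definition. That is fair: it says nothing about correlation and adds no weight to the coverage argument. It is included because the same paragraph of 9.1 would settle it.

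**Conclusion.** The concern holds and should be fixed. The stated rule ignores clustering for the primary performance endpoint, and the plan's own interval confirms that lesions are treated as independent. Under-coverage appears only when multi-lesion subjects are common and their outcomes correlate. Among the 40-lesion layouts at 65% success, coverage is never more than about a quarter of a point below nominal with 30 or more subjects and ICC up to 0.5. For 20 two-lesion subjects it is 94.3% at ICC 0.3 and 92.3% at ICC 0.5. Confidence is medium because lesions per subject and ICC are assumed. The consequence is overstated precision in a descriptive report, not a wrong decision.

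**What to change.** In 9.1, name the unit of every proportion and prespecify a cluster-adjusted interval for the lesion-level ones. One workable text:

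> Technical success and IVL technical success are analyzed per lesion with the subject as the cluster. The two-sided 95% CI is Clopper-Pearson at the Korn-Graubard effective sample size, n_eff = (n/deff) × [t(0.975, n−1)/t(0.975, S−1)]², capped at n. Here n is the number of lesions, S the number of subjects, and deff the subject-cluster-robust variance of the proportion divided by p(1−p)/(n−1), with a floor of 1. The robust variance is S/(S−1) × Σ(y_i − m_i p)²/n², where subject i has y_i successes in m_i lesions. If the observed proportion is 0% or 100%, deff = n/S. Subject-level proportions (30-day MAE, and Procedural success across all target lesions) use plain Clopper-Pearson. Counts are reported by lesion and by subject, with the distribution of lesions per subject.

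Also state the unit for 12-month patency, TLR at each time point, and MAE at 6 and 12 months, which this text leaves open. In 9.2, note that [48.3, 79.4] assumes independent lesions. Reconcile the name and unit of Procedural success across 5.2, 9.2 and 15.1.

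**Cost.** The drafting is a paragraph in 9.1, the note and wording corrections in 9.2 and 15.1, and a few lines of code. If made as a protocol amendment, it also goes to the ethics committees under 11.6. With one lesion per subject, the robust variance equals p(1−p)/(n−1) and S = n, so n_eff = n and the result is the plain exact interval. If lesions are truly independent, mean width at 65% success rises from 30.7 points to 31.5, 31.9, 33.2 or 34.7 with 35, 30, 20 or 14 subjects. At 90% success it rises from 20.3 points to 20.7, 21.0, 21.9 or 23.2.
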